5.2. HeroTracker

A wireless Bluetooth-enabled inhaler sensor that tracks medication dosage and adherence. Designed for both controller and rescue medications in diskus and MDI formats.

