6. STUDY DESIGN

This is a prospective, randomized, controlled study of children with persistent asthma who are managed on daily inhaled corticosteroids (ICS). 75 children will be randomized **2:1** into one of two arms:

- 50 children will be randomized to BreatheSmart, comprised of:
 - BreatheSmart mobile application that tracks medication usage and sends real time reminders
 - HeroTracker sensor that counts dosage and monitors real-time medication adherence
 - CoheroConnect provider portal that allows the Investigator to monitor real-time adherence and to provide targeted outreach to children with low adherence (intervention arm)
- 25 children will be randomized to “standard of care” (control arm). These patients are reminded to adhere to the prescribed standard of care therapy provided by their clinician during their clinical encounters and when the family calls to report an illness.

6.1.Endpoints

6.1.1 Primary:

The study's primary objective is to estimate the relative improvement in medication adherence among children using BreatheSmart with feedback compared to control at 6 months.

6.1.2 Secondary:

Important secondary objectives include the extent to which BreatheSmart system improves the following when compared to control from baseline to 6-months:

- asthma control as measured by the Childhood Asthma Control Test (ACT)
- lung function as measured by FEV1 and FEV1/FVC ratio compared to standard of care
- the correlation between changes in medication adherence and changes in FEV1 and FEV1/FVC ratio.
- the overall number of provider visits for asthma related adverse events (number of exacerbations leading to acute Provider intervention, ER visits, hospitalizations, or requiring oral systemic corticosteroid therapy)
- number of missed school days

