7. STUDY POPULATION

This study will enroll children who have been diagnosed with persistent asthma for at least 6 months' duration and who are showing evidence of poorly controlled disease. 75 children will be recruited from CT Children's Medical Center Pulmonary Clinic and East and West Primary Care.

7.1.Inclusion and Exclusion Criteria

Inclusion and Exclusion Criteria

Inclusion criteria:

- Age 8 to 17
- Diagnosis of persistent asthma
- Prescribed an inhaled corticosteroid (ICS) for at least one month prior to enrollment
- Use of a pressurized metered dose inhaler (pMDI) compatible with the Cohero mHealth Herotracker (See Appendix)
- Parent/child possess a compatible smartphone (iOS 8.0 or higher)
- English or Spanish speaking

Exclusion criteria:

- Presence of another chronic lung disease or condition such as cystic fibrosis, interstitial lung disease, chronic lung disease of prematurity, recurrent aspiration, or presence of tracheostomy
- Presence of other chronic medical condition such as congenital heart disease or immunodeficiency
- Presence of other comorbidities that, in the opinion of the investigator, will interfere with collection of study procedures, or limits life expectancy to < 1 year
- Currently pregnant or planning to become pregnant during the trial period

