7.2. Sample Size Estimates

There is no pilot data available to inform a sample size analysis. In addition, our sample size is limited by our supply of HeroTracker devices (50). As this is an exploratory study, we hope our findings will inform future sample size analyses for studies of similar focus with a larger cohort.

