8.2. Randomization

If the child is eligible and they wish to participate they will be randomized in a 2:1 allocation to BreatheSmart or to standard of care. As we have a limited supply of HeroTracker devices and the CoHero platform does not provide a feasible way to execute any degree of blinding, this will be conducted as an open trial where both groups (control and intervention groups) will be treated as equally as possible. Randomization will be stratified by age at the time of enrollment (8-13 years, 14-17 years) and blocked in randomly permuted sequences of 4.

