8.3.2. Active Participants

Active participants will be reminded to adhere to the standard of care therapy, as prescribed. They will be trained to and provided with the BreatheSmart application and Herotrackers. The following assessments will be recorded:

- Concomitant medications
- Measurement of lung function including FEV1, FEV1/FVC ratio, FEF25-75, FeNO (standard clinic measurement, completed by participants recruited for the pulmonary clinic)
- Child Asthma control test (ACT) questionnaire
- Exacerbation of asthma episodes (obtained through self-report and chart review) requiring:
 - Courses of oral steroids
 - Doctor visits outside of standard of care
 - ER visits
 - Hospitalizations
- Missed school days
- PedsQL asthma module (patient and parent report)
- Test of Adherence to Inhalers
- Pharmacy refill data for asthma prescriptions during the previous 6 months

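### Section 8.2 pairs 2:1 allocation with permuted blocks of 4, but no block of 4 is 2:1 and no mixing rule is given

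*Combined protocol and SAP*

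**What the plan says.** Section 8.2 (Randomization) says of eligible, willing children that "they will be randomized in a 2:1 allocation to BreatheSmart or to standard of care". The same section stratifies by two age groups (8-13 and 14-17 years) and says the list is "blocked in randomly permuted sequences of 4". Four is the only block length given.

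Section 6 (Study Design) turns the ratio into arm sizes: "50 children will be randomized to BreatheSmart, comprised of" the app, the sensor and the provider portal, and 25 go to standard of care, out of 75. Section 7.2 says that the sample size is limited by a supply of 50 HeroTracker devices, that no pilot data exist, and that the study is exploratory. No power is stated.

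The number of devices per active child is not given. Section 8.3.2 says these children are "provided with the BreatheSmart application and Herotrackers", in the plural, and Section 5.2 describes the sensor as "Designed for both controller and rescue medications in diskus and MDI formats".

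No section gives the composition of a block of 4, a rule for mixing compositions, a second block length, or a separate randomisation specification. Section 10.4 refers to a SAP still to be developed, but for data analysis only.

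**The concern.** The two instructions in Section 8.2 cannot both hold within any one block. Whoever builds the list has to supply a rule that the protocol does not contain, and the arm sizes depend on which rule is chosen. At stake are:

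- the stated ratio and the 50/25 split;
- the precision of the between-arm comparison;
- possibly the device supply, since 50 devices equals the planned active arm exactly if each child uses one;
- reproducibility, since Section 10.4 says the results may inform the design and sample size of a larger study, so readers need to know the allocation actually used.

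**Working it through.** **Inputs.** N = 75 (Sections 6 and 7); ratio 2:1 (Sections 6 and 8.2); block length 4 and two age strata (Section 8.2); 50 devices (Section 7.2).

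**1. The plan's own figure.** 75 × 2/3 = 50 and 75 × 1/3 = 25. The 50/25 split is consistent with 2:1. The defect lies only in the block rule.

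**2. Can a block of 4 be 2:1?** Active children needed per block: 4 × 2/3 = 2.67. The possible compositions are 4:0, 3:1, 2:2, 1:3 and 0:4. None is 2:1. A block of length b can be exactly 2:1 only if 2b/3 is a whole number, so b must be a multiple of 3.

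**3. One fixed composition throughout.** With two strata totalling 75, there are always 18 complete blocks (72 children) and 3 children in incomplete blocks, split 0+3 or 1+2 between the strata.
- All 3:1: 18 × 3 = 54 active, plus 1 to 3 from the incomplete blocks, gives 55-57.
- All 2:2: 18 × 2 = 36 active, plus 0 to 3, gives 36-39.

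Neither range contains 50.

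**4. Mixtures.** More than one mixture averages two thirds active:
- 3:1 with weight 2/3 and 2:2 with weight 1/3: 2/3 × 3/4 + 1/3 × 1/2 = 2/3.
- 4:0 with weight 1/3 and 2:2 with weight 2/3: 1/3 × 1 + 2/3 × 1/2 = 2/3.

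So the text does not determine the list even if a mixture is presumed. The table gives the simulated number active among 75. The younger stratum's share is an assumption; shares of 0.5, 0.6 and 0.7 give nearly the same results.

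| Scheme | Mean | SD | More than 50 active |
|---|---|---|---|
| 3:1 or 2:2 drawn independently (2/3, 1/3) | 50 | about 2.1 | about 42% |
| 3:1, 3:1, 2:2 in random order per set of 12 | 50 | about 0.76 | about 24% |
| Blocks of 6 (4:2), for comparison | 50 | about 0.72 | about 24% |

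The last two schemes both have a range of 48-52 active.

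**5. Precision.** *Assuming equal SDs in the two arms and outcome data from every child*, confidence interval width is proportional to √(1/n₁ + 1/n₀).
- 50/25: √(1/50 + 1/25) = 0.2449.
- 55/20: 0.2611, ratio 1.066. 57/18: 0.2704, ratio 1.104. All-3:1 is about 7-10% wider.
- 36/39: 0.2311, ratio 0.944. All-2:2 is about 6% narrower.

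Equal SDs cannot be presumed, because Section 8.4 takes control adherence from refill records and self-report while active children are also monitored by sensor. Let the control SD be k times the active SD, so that width is proportional to √(1/n₁ + k²/n₀), with k from 0.5 to 2 (assumed range).
- All-3:1 runs from 1% wider (55/20, k = 0.5: 0.1751/0.1732 = 1.011) to 15% wider (57/18, k = 2: 0.4897/0.4243 = 1.154).
- All-2:2 runs from 7% wider (36/39, k = 0.5: 0.1849/0.1732 = 1.068) to 15% narrower (36/39, k = 2: 0.3610/0.4243 = 0.851). At 37/38 these are 6% wider and 14% narrower.

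The sign of the all-2:2 effect therefore depends on an SD ratio that the documents do not give.

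**The case against.** The strongest reply is that Sections 6 and 8.2 already exclude the fixed-composition lists. A statistician who honours the 2:1 and the 50/25 is left with mixtures that average 50 active. The orderly one (3:1, 3:1, 2:2 in random order) behaves almost exactly like blocks of 6, so on that reading changing the block length gains very little. This stands as far as it goes, and it makes a written rule for length 4 as good a remedy as a new length. It does not remove the conflict. The text neither mentions a mixture nor chooses between them, the possible mixtures spread differently, and a literal list with one composition per block remains an easy mistake.

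The device argument is weak as support for one fix over another. It needs one device per child, which the documents do not state. With more than one each, 50 devices do not cover 50 children under any block size. With one each, blocks of 6 still put more than 50 children in the active arm in about 24% of runs.

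Three stronger readings are tempting, and the documents support none of them:

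- **That the comparison is invalid or biased.** Every list considered here is still randomised within strata. The wrong block size changes the ratio, not the validity.
- **That the trial will in fact enrol 55-57 active children and run out of devices.** That follows only if an all-3:1 list was built and each child uses one device. The documents establish neither.
- **That randomisation would stop at the 50th active child, leaving a smaller control arm.** The protocol contains no such rule, so no precision loss should be calculated from it.

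**Conclusion.** The point holds. Section 8.2 is wrong as written rather than merely brief: its only block length cannot deliver its stated ratio, and any single composition misses 50/25 (55-57 or 36-39 active). That result is integer arithmetic and needs no assumption beyond 75 children in two strata.

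The consequence is modest. The study is exploratory, with no stated power to lose. The effect is confined to the arm ratio and precision, and to device supply only if each child uses one device. The mixture figures rest on assumed stratum shares, to which they are insensitive. The interval-width figures hold only under the stated SD ratio and complete outcome data, and should not be quoted without those conditions. This should be corrected because the error is certain and the correction cheap, not because it threatens the trial.

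**What to change.** Amend Section 8.2 in one of two ways; they are equally valid.

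1. **Change the length.** Replace the block-of-4 wording with: *within each age stratum, allocation uses randomly permuted blocks, each exactly 2:1, with lengths that are multiples of 3 and are not disclosed to recruiting staff.* The list specification can then use blocks of 6, or 3 and 6 in random order; either gives 48-52 active of 75. Blocks of 3 alone hold the arm size more tightly (49-51). However, the trial is open, and if the size became known 44% of assignments would be fully determined, against 29% for blocks of 6.
2. **Keep length 4 and state the composition rule.** For example: *within each age stratum, each set of 12 consists of two 3:1 blocks and one 2:2 block in random order.* This also gives 48-52 active.

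Under either option, incomplete final blocks can still give 51 or 52 active, so the sponsor should also state the number of devices per child and reconcile it with the supply of 50.

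The cost is one sentence and, before enrolment, a regenerated list. If enrolment has begun, document the scheme actually used, including any mixture of compositions, and report the true ratio.

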8.3. Baseline Assessments

8.3.1. Control Participants

Control participants will be reminded to adhere to the standard of care therapy, as prescribed. The following assessments will be recorded:

- Concomitant medications

- Measurement of lung function including FEV1, FEV1/FVC ratio, FeNO (standard clinic measurement only assessed in the Pulmonary clinics)
- Child Asthma control test (ACT) questionnaire
- Exacerbation of asthma episodes (obtained through self-report and chart review) requiring:
 - Courses of oral steroids
 - Doctor visits outside of standard of care
 - ER visits
 - Hospitalizations
- Missed school days
- PedsQL asthma module (patient and parent report)
- Test of Adherence to Inhalers
- Pharmacy refill data for asthma prescriptions during the previous 6 months

8.3.2. Active Participants

Active participants will be reminded to adhere to the standard of care therapy, as prescribed. They will be trained to and provided with the BreatheSmart application and Herotrackers. The following assessments will be recorded:

- Concomitant medications
- Measurement of lung function including FEV1, FEV1/FVC ratio, FEF25-75, FeNO (standard clinic measurement, completed by participants recruited for the pulmonary clinic)
- Child Asthma control test (ACT) questionnaire
- Exacerbation of asthma episodes (obtained through self-report and chart review) requiring:
 - Courses of oral steroids
 - Doctor visits outside of standard of care
 - ER visits
 - Hospitalizations
- Missed school days
- PedsQL asthma module (patient and parent report)
- Test of Adherence to Inhalers
- Pharmacy refill data for asthma prescriptions during the previous 6 months

8.4. Follow-up

All participants in both groups will be seen at 90 and 180 days' post randomization (+/-20 days) correlating with routine pulmonary clinic follow up and East and West Primary Care Follow up where the following assessments will be recorded:

- Medication changes/refills (obtained through pharmacy record)

- FEV1, FEV1/FVC, FEF25-75 and FeNO per clinical standard of care (only assessed in the Pulmonary clinic)
- Child Asthma control test (ACT) questionnaire
- Serious Adverse Events will be recorded at each visit
- Missed school days
- PedsQL asthma module (patient and parent report)
- Test of Adherence to Inhalers
- Exacerbation of asthma episodes (obtained through self-report and chart review) requiring:
 - Doctor visits outside of standard of care
 - ER visits
 - Hospitalizations

In addition, active participants (test group) will be continuously monitored via the CoheroConnect dashboard which allows the Investigator to monitor the child's medication adherence in real time. If a period of participant inactivity of 3 days is registered in the system, the Investigator (or designee) will be notified and he/she will be prompted to contact the participant to remind them to take their medication as prescribed. The Investigator or designee will review patient specific data (% adherence since last visit and graph of adherence patterns over time since enrollment) through the CoheroConnect dashboard within two days before a follow up visit. At the follow-up visit, these data will be reviewed with the patient and parent/caregiver. The adherence rate and barriers identified will be discussed and, if necessary, personalized strategies for improvement will be devised. These data will also be shared with the clinician during these follow up visits. Medication adherence data for control participants will be obtained by measure of pharmacy record refill information and self-report (Test of Adherence to Inhalers) throughout the duration of the study.

We understand that the self-report of missed school days due to asthma may be unreliable and subject to recall bias, however, this is the method we currently use clinically to assess this measure.

If a participant is unable to complete the follow-up visit at their routine pulmonary appointment, the coordinator will either mail, text a link, or email a link of the follow-up surveys to the participants. They will be reminded 3 times via text, email or phone to complete the follow-up questionnaires.

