10.4. Data analysis

All data will be analyzed in accordance with the statistical analysis plan (SAP) to be developed at the beginning of this study. Both primary and secondary analyses will be based on an intention-to-treat (ITT).

The study's primary objective is to estimate the relative improvement in medication adherence among children using the BreatheSmart compared to control participants using "standard of care".

Important secondary objectives include the extent to which the Cohero system improves:

- asthma control as measured by ACT

- FEV1, FEV1/FVC ratio, FEF25-75 and FeNO compared to standard of care, and the correlation between changes in medication adherence from baseline and changes in FEV1 and FEV1/FVC ratio.
- the overall number of provider visits for asthma-related adverse outcomes (number of exacerbations leading to Provider intervention, ER visits, hospitalizations, or requiring oral systemic corticosteroid therapy)
 - Missed school days

Data results may be used to inform a study of a larger cohort with similar focus with regard to sample size estimates, efficacy of the BreatheSmart platform, feasibility in a low-income pediatric population and study design.

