10.5. Statistical Analysis

Between group differences in the change in mean adherence from baseline over will be based on a 0.05 level t-test. The corresponding 95% confidence interval for the between group mean difference will provide an interval estimate of benefit obtained using the Cohero system. [NR1]

In addition to the frequentist analysis of adherence, a Bayesian approach that focuses on estimating the probability distribution of differences in mean adherence using the Cohero system compared to standard of care. The Bayesian approach begins with the premise that the Cohero system yields no improvement in adherence. This is an exact correspondence to a “null hypothesis”. This assumption is incorporated through a prior distribution for improvement in mean adherence; for example, by assuming that the mean improvement is characterized by a normal distribution with mean 0, the expected difference should the Cohero system offer no benefit, and some small variance (e.g. 0.01). This is also a statement that the probability that the Cohero system improves response compared to standard of care is 50% (i.e., the prior odds that active therapy is effective is 1:1, consistent with the notion of equipoise).

The essence of the Bayesian approach is to use the data collected during the study to update the prior probability density based on the observed data (this updated density is the posterior probability distribution) using Bayes Theorem. This posterior distribution provides estimates of the probability that the Cohero system improves adherence relative to standard of care by any amount greater than δ . For example, choosing $\delta=0$ corresponds to the frequentist test of the null hypothesis.

The analysis of lung function will be performed in a corresponding manner to that described for adherence. Additionally, the correlation between change in FEV1, FEV1/FVC ratio and FEF25-75 and change in adherence will be computed. Graphical analysis will be used to visually inspect the relationship between improvement in adherence and improvement in lung function. Based on the general form of the relationship, additional exploratory analyses will be performed. For example, if the relationship is approximately linear, standard regression methods will be used to estimate the relationship; if, however, a clear discontinuity is seen, splines might be used to estimate the relationship.

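### The primary outcome, medication adherence, has no named measure, and the sentence in 8.4 on how adherence data are obtained covers control participants only

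*Combined protocol and SAP*

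**What the plan says.** Section 6.1.1 sets the primary objective: to "estimate the relative improvement in medication adherence among children using BreatheSmart with feedback compared to control at 6 months". Section 10.4 repeats it without a measure and adds "All data will be analyzed in accordance with the statistical analysis plan (SAP) to be developed at the beginning of this study". Section 10.5, the only statistical section supplied, says "Between group differences in the change in mean adherence from baseline over will be based on a 0.05 level t-test". None of the three gives an instrument, formula, unit or observation window. The example prior in 10.5, with "some small variance (e.g. 0.01", suggests a proportion scale but does not say what is being measured.

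Sections 8.3.1 and 8.3.2 list pharmacy refill data for the previous 6 months and the TAI at baseline in both arms. Section 8.4 begins "All participants in both groups will be seen at 90 and 180 days", and its list for those visits includes "Medication changes/refills (obtained through pharmacy record" and the TAI.

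Section 8.4 then describes the active arm's dashboard. Staff review the child's percentage "adherence since last visit and graph of adherence patterns over time since enrollment" before each visit. The paragraph ends with the sentence on controls: "Medication adherence data for control participants will be obtained by measure of pharmacy record refill information and self-report (Test of Adherence to Inhalers". Section 5.1 also describes the app and HeroTracker as a means of collecting adherence data.

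**The concern.** A statistician following the text has three candidate measures: refill, TAI and sensor. The one sentence that says how adherence data are obtained is restricted to controls, offers two sources, and follows directly on the active arm's sensor percentage. If refill and TAI were the outcome in both arms, a control-only sentence would hardly be needed. The natural inference is sensor data for the active arm.

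The protocol's own background (section 1) shows that the measures are not interchangeable. It cites mean controller adherence of 20 to 34% by medication possession ratio and 38 to 71% by electronic monitoring, and says that self-report overestimates. If the arms were measured differently, the t-test, its 95% confidence interval and the Bayesian posterior would all carry the instrument difference, and randomisation would not remove it. The correlation between change in adherence and change in lung function would be affected too.

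**Working it through.** The plan gives no power, effect size or SD, so there is no figure to reproduce. Its only sample-size arithmetic, 50 + 25 = 75 at 2:1, is consistent.

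**Step 1. What is collected, and what is designated.**

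| Measure | Baseline | 90 and 180 days | Named as primary outcome? |
|---|---|---|---|
| Pharmacy refill | both arms (8.3.1, 8.3.2) | both arms (8.4) | no |
| TAI | both arms (8.3.1, 8.3.2) | both arms (8.4) | no |
| Sensor | neither arm; first issued at baseline (8.3.2) | active arm only (8.4) | no |

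A common measure is available. What is missing is the designation.

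**Step 2. What a mismatch would do.** Let R be the refill value, S the sensor value, and subscripts 0 and 6 baseline and 6 months. Section 10.5 analyses change from baseline.

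- Control change: R6 − R0.
- Active change with a sensor follow-up value: S6 − R0 = (R6 − R0) + (S6 − R6).

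The between-arm difference is therefore the treatment effect on the refill scale plus an offset δ, the mean of S6 − R6. With one measure in both arms, δ = 0.

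**Step 3. A documentary anchor for δ.** From section 1:

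- Nearest ends of the two ranges: 38 − 34 = 4 points.
- Midpoints: (38 + 71)/2 − (20 + 34)/2 = 54.5 − 27 = 27.5 points.

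The two ranges may reflect different populations, so neither figure is a pure method gap. I use 4 points as the lower illustration and 10 points, an assumption, as the upper.

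**Step 4. Chance of p<0.05 with no true effect (mismatched case only).**

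- Inputs: n = 50 and 25 (section 6); level 0.05 (10.5), taken as two-sided because a 95% interval accompanies it; SD of change 20, 25 or 30 points (assumption).
- SE = SD × √(1/50 + 1/25) = SD × √0.06.
- df = 50 + 25 − 2 = 73; critical t = 1.993.
- Noncentrality λ = δ/SE. Rejection probability = 1 − F(1.993; 73, λ) + F(−1.993; 73, λ), where F is the noncentral t distribution function.

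| SD | SE | δ = 0 | δ = 4 | δ = 10 |
|---|---|---|---|---|
| 20 | 4.90 | 5.0% | 12.7% | 52.2% |
| 25 | 6.12 | 5.0% | 9.9% | 36.4% |
| 30 | 7.35 | 5.0% | 8.4% | 26.9% |

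Because the true effect is zero, coverage of the 95% interval is 100% minus these figures: 87 to 92% at 4 points and 48 to 73% at 10. A negative offset gives the same rates in the other direction. With δ = 0 the test keeps its 5% level, and the interval half-width is 1.993 × SE = 9.8, 12.2 or 14.6 points.

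**The case against.** The strongest reply is that the protocol never makes sensor data the active arm's outcome. It presents the dashboard as monitoring and feedback. Refill and TAI are scheduled in both arms, and an analysis of change from baseline favours a measure that has a baseline, which the sensor lacks. This stands. A reader might infer that the trial is committed to sensor against refill or self-report, but the documents only leave that comparison open. The error rates above therefore belong to one branch and do not describe the trial as planned.

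A reader might also infer that the measure could be picked after the results are seen. Section 10.4 places the SAP at the beginning of the study, so on the protocol's own schedule the choice comes before 6-month data exist. What remains is that the protocol names no measure, section 10.5 does not supply one, and 8.4 gives whoever writes the SAP a sentence that treats the arms differently.

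Section 7.2 calls the study exploratory. That moderates the consequences, but 10.5 still specifies a 0.05-level test, and 10.4 says that the results may inform the sample size and efficacy expectations of a larger study. An offset would be carried into that study.

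**Conclusion.** The concern holds as a missing designation. The primary outcome has no named measure, and the control-only sentence in 8.4 points towards different instruments in the two arms without committing to them. This needs correcting, because the primary result cannot be interpreted until its measure is known.

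The size is conditional. If the arms were measured differently, an offset of 4 to 10 points would raise the false-positive rate from 5% to between 8 and 52%, given an SD of change of 20 to 30 points and a constant offset that falls wholly on the active arm's change. The SDs and the 10-point offset are assumptions. The 27.5-point midpoint gap should not be read as the expected bias, because the cited ranges may come from different populations. The direction is also not fixed: the section 1 ranges suggest that sensor against refill would favour the device, while self-report in controls, which section 1 says overestimates, would work against it. If one measure is used in both arms, this bias is absent.

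**What to change.** In 6.1.1, 8.4 and 10.5, and in the SAP due at the start of the study, name one primary adherence measure obtained the same way in both arms at baseline and 6 months. ICS refill adherence from pharmacy records is the natural choice, because it is already scheduled in both arms and is not self-report. Any single common measure would remove the offset. A sensor for every child is not feasible: 75 children against a supply of 50 devices (7.2).

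Replace the control-only sentence in 8.4 with:

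*Adherence outcome data for both arms are obtained from pharmacy refill records (primary) and the Test of Adherence to Inhalers (secondary); HeroTracker data are not used in the between-arm comparison.*

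The sponsor should set the refill formula identically for both arms. It must cover the observation window in relation to the ±20-day visit window, and supply carried over from before randomisation.

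The cost should be low, since no new type of data is needed. The documents do not say that fill dates and days' supply are captured, so this should be confirmed. Two downsides remain. Refill is coarser than the sensor. Baseline values will also be unstable in children with only about one month of prior ICS, the minimum in 7.1: if a fill covers 30 days (assumption), one fill is 30/30 = 100% of a 30-day window but 30/180 = 17% of a 180-day window. Randomisation balances this in expectation, so it adds noise but not bias.
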